3.4.4 Focus group discussions with selected community groups

Focus group discussions will be organized with members of the community regardless of their experience with the use of ePOCT+ for clinical consultation. This is meant to gather unbiased opinions, perceptions, and attitudes of community members toward the use of ePOCT+ and digital health tools in general. The tools for the interviews and focus groups can be found in **Appendix 2**.

3.4.5 In-depth interviews with members of the CHMTs

Development and implementation of the medAL-monitor and the medAL-outbreak tools will be done in close collaboration with the district team and the HMIS department of the MoH from the very beginning. Once implemented, members of the CHMT will be interviewed about the impact of medAL-monitor on their ability to supervise and mentor HF staff. Similar interviews will be conducted with members of the HMIS department responsible for surveillance regarding the impact of the medAL-outbreak tool on their ability to detect and manage outbreaks. For example, they may be asked if the respective tool is accessible with internet connectivity available to them, if the indicators displayed in the dashboards are relevant and appropriate, and if the information displayed is clear, easily interpretable, and actionable. The interviews may be conducted several times for the purpose of continuous improvement of the tools and for final evaluation of their effectiveness. The tools for the interviews and focus groups can be found in **Appendix 2**.

3.4.6 Economic and ecological evaluations

Ecological and human impact

An ecological and human impact evaluation of the project will be assessed in collaboration with the “Sustainability Center” and the “Institute of Earth Surface Dynamics” of the University of Lausanne, to ensure that the intervention has limited impact on (or is even beneficial to) the environment and global warming. Indeed, the CO₂ emissions and pollution due to the manufacturing and use of tablets might be lower than that due to the manufacturing and international and national transport of (unnecessary) antibiotics and HF re-attendance visits or hospitalizations. Life Cycle Analysis (LCA) is a systematic study of the environmental impacts of product systems, which analyzes energy and material flows during the whole life cycle: extraction and acquisition of raw material, use, end-of-life treatment and final waste disposal (Frischknecht et al. 2007). Through such a systematic perspective, the displacement of potential environmental loads between the different stages of the life cycle or between

particular processes can be identified and avoided. The International Organization for Standardization published international standards on LCA, which gives a framework for LCA and guarantees the transparency of the analysis (see ISO 14040; 2006A and 2006B). This methodology is fully applicable to a project development.

Cost analysis

Cost analysis will compare the cost of care provision under routine conditions and with the use of ePOCT+. Costs will include costs to patients, providers, health system, and project implementation (Yukich et al. 2010). Costs of resource inputs for providers will be determined on the basis of the Tanzania current pharmaceutical and supply price list and interviews with the appropriate financial managers of the Dar es Salaam City Medical Office of Health. Patient costs will be valued according to self-reported expenditures and lost income due to the travel to and time spent in the HF. Costs of project implementation will include tablets and the associated IT infrastructure, initial and refresher trainings and supervisory visits, additional laboratory tests, but will exclude specific research costs.

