| | 
 - Concordance between final diagnoses as proposed by ePOCT+ and final diagnoses by HCW (intervention HFs only) 
Objective 2 (Improve the algorithm and adapt it to spatiotemporal variations):
 
 - Number of positive impact modifications in the algorithm identified by ML analyses - - Number of positive impact modifications tested through randomized sub-studies - % of these positive impact modifications confirmed to be safe and useful by randomized sub-studies - Number of modifications implemented, by type of impact (better clinical cure, less severe clinical outcomes, less medicines or diagnostic tests needed, shorter consultation time) 
Objective 3 (Enhance disease surveillance and outbreak detection):
 
 - Number of indicators related to disease surveillance and outbreak detection based on individual data that can be visualized through the medAL-outbreak dashboard - Average delay between the date of recording of clinical data and the date they are available on medAL-outbreak - Number and type of epidemic alerts raised by the medAL-outbreak tool - % of these epidemic alerts registered by the district authorities for epidemic response 
Objective 4 (Enhance M&E and supportive supervision and mentorship):
 
 - Number of M&E indicators based on individual data that can be visualized through the medAL-monitor dashboard - Number of supervision and mentorship visits to HFs facilitated by the medAL-monitor tool - Number of CHWs reporting having used the medAL-monitor tool for self-auditing their clinical practices - Number of CHWs and members of CHMT reporting a positive experience with the medAL-monitor tool 
Objective 5 (Create a supportive environment for the use of clinical algorithms and disease surveillance tools):
 
 - Number of sick children attending primary care facilities managed by HCWs using the electronic ePOCT+ tool - % of CHWs able to assess key clinical signs - Frequency of use of medAL-outbreak by district team members - Frequency of use of the medAL-monitor tool by district team members - Perception by HCWs of the ePOCT+ tool and intervention and the number of improvements they propose for the tool or intervention - Perception by caregivers and community members of the intervention and the number of improvements they propose - Perception by district team members of the medAL-outbreak tool and the number of improvements they propose for the tool - Number of medical experts able to modify a clinical algorithm using MedAL-Creator - Number of computer scientists able to maintain the software and the IT infrastructure for clinical algorithms - Number of scientists able to analyze clinical data using ML - Number of local students trained in applied ML for health care in resource-limited settings - Perception of the current and future utility of ML to improve health care amongst clinical experts (deciding on algorithm changes) and health authorities - Patient and provider expenditures related to care of acutely ill children included in the study |

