4 STUDY AREA

4.1 Study sites

This study will be conducted in the Morogoro region (Mlimba, Ifakara and Ulanga districts) and in the Mbeya Region (Mbeya rural district and Mbeya city council) of Tanzania (**Figure 6**). Key health indicators of the selected regions compared to national average are outlined in **Table 1**. Since the previous randomized efficacy study was performed in urban primary health care centers in Dar es Salaam, we chose rural and semi-urban areas to extend the generalizability of the evaluation of the intervention. To evaluate whether the effect of the intervention varies depending on the level of malaria transmission, we chose areas with low (Mbeya rural district, Mbeya city council) and moderate (Mlimba, Ifakara and Ulanga districts) malaria endemicity. A direct train connection between Ifakara and Mbeya (TAZARA) will facilitate travel of investigators between the two sites.

Both, Ulanga and Mlimba Districts are found in the South-eastern region of Tanzania. Ulanga DC has a population of 265'000 inhabitants while Mlimba DC, which was previously called Kilombero DC has a population of 410,783 with the headquarters in Mngeta. Ifaraka Town Council is part of Mlimba DC with its own administration. Main economic activities in the two districts is subsistence farming mainly rice and smaller proportion of pastoralists who migrated from the north and center of the country. Most economic activities in Ifakara Town Council include agricultural trades, farming and provision of higher education in the biomedical field.

Mbeya DC is among seven districts of Mbeya region in the Southern highlands of Tanzania with a population of 366,986, with the headquarters in Inyala and a total of 74 total health facilities. The main economic activities are subsistent farming (commercial and food crops) and livestock keeping. Mbeya city is estimated to have a population of 471,971 by 2018, and it is the capital, commercial city of Mbeya.

Figure 6: Map of Africa and Tanzania (A) with study regions (B) and districts (C and D) highlighted.

[figure not shown]

Table 1: Key indicators of child health in Morogoro and Mbeya regions

| Indicator | Morogoro region | Mbeya region | National average |
|--|-----------------|--------------|-----------------------|
| Under five mortality rate (per 1000 live births) ¹ | 163 (2002) | 165 (2002) | 153 (2002), 81 (2010) |
| Malaria prevalence in children aged 6-59 months (2017) ² | 9.5% | 4.0% | 7.3% |

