4.2 Selection of health facilities

PHC facilities are defined as the first point of contact to seek curative services. Facilities eligible for randomization in phase 1 will be determined in collaboration with the Regional Health Authorities prior to the start of the study. Permission for facility participation in the study and agreement to implement care practices as per randomization assignment at the level of the facility will be ascertained from HF administrative leadership prior to randomization. In phase 1, we anticipate enrolling 40 HFs (20 per arm), 24 in the Morogoro Region and 16 in the Mbeya Region. In phase 2, we plan to enroll 60 additional HFs, to reach a total of around 100 HFs.

Inclusion Criteria:

- Government and private government-designated Primary care HFs (health posts, dispensaries and health centers).
- Located in the Mlimba, Ifakara and Ulanga districts (Morogoro Region) or in Mbeya Rural district and Mbeya city council (Mbeya Region).
- Seeing at least 20 children aged 2 months to 5 years per week on average over the past 6 months (to facilitate participant recruitment).

Exclusion Criteria:

- Secondary and Tertiary HFs (district, regional, zonal and specialized hospitals).

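### Provider costs not on the national price list are to come from a Dar es Salaam office, although every study facility is in Morogoro or Mbeya

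*Protocol*

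**What the plan says.** Protocol section 3.4.6 (Cost analysis) compares the cost of care under routine conditions and with ePOCT+. It lists four kinds of cost: patient, provider, health system and project implementation. Their sources differ.

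- **Provider inputs, first source.** "Costs of resource inputs for providers will be determined on the basis of the Tanzania current pharmaceutical and supply price list".
- **Provider inputs, second source.** "interviews with the appropriate financial managers of the Dar es Salaam City Medical Office of Health".
- **Patient costs.** "Patient costs will be valued according to self-reported expenditures and lost income due to the travel to and time spent in the HF".
- **Project implementation.** "Costs of project implementation will include tablets and the associated IT infrastructure", and also training, supervisory visits and additional laboratory tests. No office is named as the source.

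On location, section 4.1 states: "This study will be conducted in the Morogoro region (Mlimba, Ifakara and Ulanga districts) and in the Mbeya Region". It explains that the previous randomized trial was done in urban Dar es Salaam and that, for this reason, "we chose rural and semi-urban areas to extend the generalizability of the evaluation of the intervention". Section 4.2 makes location in Mlimba, Ifakara, Ulanga, Mbeya Rural or Mbeya city an inclusion criterion for facilities.

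The quantity to be reported appears among the Objective 5 indicators in the Synopsis and in section 7.5: "Patient and provider expenditures related to care of acutely ill children included in the study".

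**The concern.** The indicator concerns spending on children enrolled in the study, and all of them are seen in Morogoro or Mbeya. The only office named for interview-based provider costs serves a city with no study facility, and it is the city the investigators chose to move away from so that the results would apply elsewhere. If the text is followed literally, part of the provider cost will describe a setting in which no study child is treated.

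What is at stake is the credibility of the provider-cost figures for the study area. Section 12.2 says the economic evaluation will give the overall cost of care with and without ePOCT+, next to trial evidence meant to support guidelines for national scale-up. Readers of those figures would take them to describe the districts where the study was run.

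**Working it through.** The plan states no cost figure, so there is nothing to reproduce. The check sets the source of provider costs against the location of the facilities, then asks where a price error could act.

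**1. Is any facility in Dar es Salaam?** No. Section 4.2 plans 40 facilities in Phase 1, 24 in Morogoro and 16 in Mbeya (24 + 16 = 40), so none are left over. The up to 60 facilities added in Phase 2 are described in section 3.2 as neighbours within the same target area, and the location criterion in section 4.2 names the same five districts or councils.

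**2. Does other text correct or explain the source?** No.
- Section 8.5.1 says a cost will be assigned to each procedure but gives no source of unit costs.
- Sections 1.7 and 12.2 announce the cost analysis without sources.
- The SAP covers the medAL-mentor study and contains no cost analysis.
- Section 11.1 places the data server in Dar es Salaam. That is no reason to price facility care there.

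**3. Which costs are exposed?**

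| Cost category | Source in section 3.4.6 | Tied to the Dar es Salaam office? |
|---|---|---|
| Provider inputs on the price list | National list | No |
| Provider inputs not on the price list | Interviews with the city office | Yes |
| Patient costs | Self-report by families | No |
| Health system | None stated | No |
| Project implementation | Components listed, no office named | No |

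Only the second row is exposed.

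**4. What would a price error do?** For an exposed input k, let p be its true local unit cost, e the error from using a Dar es Salaam value, and q1 and q0 the quantities per child with ePOCT+ and with routine care.

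- Expenditure reported in one arm: sum of (p + e) × q. The error is the sum of e × q. The Objective 5 indicator is an expenditure, so this error does not cancel.
- Incremental cost: sum of (p + e) × (q1 − q0). The error is the sum of e × (q1 − q0). It is zero for an input used equally in both arms. Otherwise it is proportional: if the unit cost is wrong by a fraction r, so that e = r × p, the incremental cost of that input is wrong by the same fraction r.

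The protocol itself allows q1 and q0 to differ. Section 10.1 treats consultation time as a resource that may change, and section 12.2 expects fewer re-attendances and secondary admissions.

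**5. How large is e?** It cannot be calculated. The documents give no unit cost for any place, no share of provider cost that would be priced by interview, and no comparison of Dar es Salaam with the study area. The sign of e is equally unknown.

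**The case against.** The strongest reply is that little depends on this phrase. The Dar es Salaam office is one of two sources for one of four cost categories. Section 12.2 expects lower medicine costs, and medicines fall under the national price list. A common unit price would apply to both arms. Costing is one of many Objective 5 indicators. It is neither a primary nor a secondary Phase 1 outcome, and it has no test or decision rule.

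Most of this stands, and it sets the weight of the point. The argument about a common price stands only in part: the error drops out of the difference where the arms use equal quantities, but it stays in the reported expenditure of each arm.

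Three stronger readings are tempting, and the documents do not support them.

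- *The whole cost comparison is priced in the wrong place.* It is not. Patient costs and price-list items have their own sources, and implementation costs are not linked to the city office.
- *The error is larger in the ePOCT+ arm because of its extra training and supervision.* Section 3.4.6 puts training and supervisory visits under project implementation, for which no Dar es Salaam source is named. Patient travel is self-reported. No larger error in one arm is shown.
- *The wording was carried over from earlier Dar es Salaam work.* The malaria rapid-test costing study cited in the same paragraph was set there, according to its title, so this is plausible. It remains an inference.

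**Conclusion.** The mismatch is real and can be seen from the text alone: provider inputs not on the national price list are to be valued through an office outside the study area, and nothing in the protocol or SAP justifies or corrects this. The consequence is limited to the local validity of part of the provider-expenditure indicator and, for inputs that the arms use in different amounts, of the incremental cost.

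This rests on two assumptions: that some provider inputs are in fact missing from the price list and would be priced by interview, and that Dar es Salaam values may differ from those in Morogoro and Mbeya. The documents settle neither, so no percentage can be attached to the distortion and no direction stated. The point deserves correction because the fix is specific and cheap. It does not affect the Phase 1 primary comparison.

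**What to change.** In section 3.4.6, replace the Dar es Salaam office with the finance managers or health management teams of the study councils (Mlimba, Ifakara, Ulanga, Mbeya Rural and Mbeya city) as the interview source for provider inputs not on the national price list. If Dar es Salaam values are to be used at all, give the reason and confine them to a labelled sensitivity scenario. Valuing inputs separately by council is optional, and the defect does not require it.

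The cost is one change of protocol wording and a few local interviews in place of one city office. The study already has the contacts: section 8.5.2 reports that the health teams of Ifakara, Kilombero (according to section 4.1 the former name of Mlimba) and Mbeya district have been approached, and section 3.4.5 plans interviews with council health management teams. The change is cheapest before unit costs are collected. If the Dar es Salaam interviews have already been held, they can serve as the sensitivity scenario, but local ones would still be needed.

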4 STUDY AREA

4.1 Study sites

This study will be conducted in the Morogoro region (Mlimba, Ifakara and Ulanga districts) and in the Mbeya Region (Mbeya rural district and Mbeya city council) of Tanzania (**Figure 6**). Key health indicators of the selected regions compared to national average are outlined in **Table 1**. Since the previous randomized efficacy study was performed in urban primary health care centers in Dar es Salaam, we chose rural and semi-urban areas to extend the generalizability of the evaluation of the intervention. To evaluate whether the effect of the intervention varies depending on the level of malaria transmission, we chose areas with low (Mbeya rural district, Mbeya city council) and moderate (Mlimba, Ifakara and Ulanga districts) malaria endemicity. A direct train connection between Ifakara and Mbeya (TAZARA) will facilitate travel of investigators between the two sites.

Both, Ulanga and Mlimba Districts are found in the South-eastern region of Tanzania. Ulanga DC has a population of 265'000 inhabitants while Mlimba DC, which was previously called Kilombero DC has a population of 410,783 with the headquarters in Mngeta. Ifaraka Town Council is part of Mlimba DC with its own administration. Main economic activities in the two districts is subsistence farming mainly rice and smaller proportion of pastoralists who migrated from the north and center of the country. Most economic activities in Ifakara Town Council include agricultural trades, farming and provision of higher education in the biomedical field.

Mbeya DC is among seven districts of Mbeya region in the Southern highlands of Tanzania with a population of 366,986, with the headquarters in Inyala and a total of 74 total health facilities. The main economic activities are subsistent farming (commercial and food crops) and livestock keeping. Mbeya city is estimated to have a population of 471,971 by 2018, and it is the capital, commercial city of Mbeya.

Figure 6: Map of Africa and Tanzania (A) with study regions (B) and districts (C and D) highlighted.

[figure not shown]

Table 1: Key indicators of child health in Morogoro and Mbeya regions

| Indicator | Morogoro region | Mbeya region | National average |
|--|-----------------|--------------|-----------------------|
| Under five mortality rate (per 1000 live births) ¹ | 163 (2002) | 165 (2002) | 153 (2002), 81 (2010) |
| Malaria prevalence in children aged 6-59 months (2017) ² | 9.5% | 4.0% | 7.3% |
| HIV prevalence (Age 15+; 2017) ³ | 4.2% | 9.3% | 7.0% |
| Pneumococcal vaccine coverage (2017) ⁴ | 81% | 67% | 99% |
| DTP - Hib - HepB ³ (Diphtheria, tetanus, pertussis, Hemophilus influenzae type B, and hepatitis B) vaccine coverage (2017) ⁴ | 110.4% (2018) | 96.3% (2018) | 99% |
| Prevalence of low hemoglobin in children (<8g/dl) ² | 4.7% | 1.4% | 3.6% |
| Percentage of children with fever within the past two weeks ² | 18.9% | 16.2% | 20.4% |

¹National Bureau of Statistics, Tanzania; available at: <http://tanzania.opendataforafrica.org/TZSOCECD2016/social-economics-of-tanzania-2016?region=1000130-mbeya&indicator=1007140-under-5-mortality-rate-deaths-per-1-000-live-births>

²Ministry of Health, Community Development, Gender, Elderly and Children (MoHCDGEC) [Tanzania Mainland], Ministry of Health (MoH) [Zanzibar], National Bureau of Statistics (NBS), Office of the Chief Government Statistician (OCGS), and ICF. 2017. Tanzania Malaria Indicator Survey 2017. Dar es Salaam, Tanzania, and Rockville, Maryland, USA: MoHCDGEC, MoH, NBS, OCGS, and ICF. Available at: <https://dhsprogram.com/pubs/pdf/MIS31/MIS31.pdf>

³Tanzania Commission for AIDS (TACAIDS), Zanzibar AIDS Commission (ZAC). Tanzania HIV Impact Survey (THIS) 2016-2017: Final Report. Dar es Salaam, Tanzania. December 2018. Available at: THIS 2007: https://phia.icap.columbia.edu/wp-content/uploads/2017/11/Tanzania_SummarySheet_A4.English.v19.pdf

⁴USAID. Tanzania Immunization Fact Sheet. July 2018. Accessed from: https://www.usaid.gov/sites/default/files/documents/1860/Immunization_Fact_Sheet_July_2018.pdf

4.2 Selection of health facilities

PHC facilities are defined as the first point of contact to seek curative services. Facilities eligible for randomization in phase 1 will be determined in collaboration with the Regional Health Authorities prior to the start of the study. Permission for facility participation in the study and agreement to implement care practices as per randomization assignment at the level of the facility will be ascertained from HF administrative leadership prior to randomization. In phase 1, we anticipate enrolling 40 HFs (20 per arm), 24 in the Morogoro Region and 16 in the Mbeya Region. In phase 2, we plan to enroll 60 additional HFs, to reach a total of around 100 HFs.

Inclusion Criteria:

- Government and private government-designated Primary care HFs (health posts, dispensaries and health centers).
- Located in the Mlimba, Ifakara and Ulanga districts (Morogoro Region) or in Mbeya Rural district and Mbeya city council (Mbeya Region).
- Seeing at least 20 children aged 2 months to 5 years per week on average over the past 6 months (to facilitate participant recruitment).

Exclusion Criteria:

- Secondary and Tertiary HFs (district, regional, zonal and specialized hospitals).

